10.3.2 Primary Efficacy Analysis

The primary efficacy endpoint is the time to loss of Secondary Patency.

Study endpoints (see [Section 4.2](#)) will be determined by the clinical decisions of the investigators except for the following events that will be adjudicated by the CEC:

- Study conduit revisions to determine whether the original study conduit was still being used for dialysis.
- Access-related infections using the Centers for Disease Control and Prevention (CDC) definitions for dialysis-associated infections ([CDC 2013](#)).

The outcome of these adjudications will be used as endpoints in the trial rather than the investigator determinations.

The primary analysis will be a non-inferiority analysis, which will be conducted when all subjects are at least 18 months post-implantation.

The primary analysis will be in the ITT population with confirmatory analyses in the mITT and PP populations.

The following rules will apply to the ITT population:

- Subjects in whom the wrong study conduit was implanted (e.g., an HAV implanted in a subject randomized to an ePTFE graft) will be analyzed within their randomized group rather than in their 'implanted' group.
- Subjects in whom no study conduit was implanted will be considered as if abandoned on Day 0 and included in their randomized group.

The hazard ratio (HAV relative to ePTFE) will be estimated using a Cox proportional hazards regression model with treatment group and the randomization stratification variable as factors. Based on the estimated 18-month event-free rate in the ePTFE arm, the non-inferiority margin will be determined by the hazard ratio corresponding to a difference of 10 percentage points. If the lower limit of the two-sided 95% confidence interval for the hazard ratio is greater than the corresponding non-inferiority bound, then non-inferiority will be demonstrated.

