Unless otherwise specified, continuous variables will be summarized by presenting the number of non-missing observations, mean, standard deviation, median, inter-quartile range, minimum and maximum. Categorical variables will be summarized by presenting the number of subjects and percentage for each category.

Unless otherwise noted, all tests of treatment effects will be conducted at a 2-sided alpha level of 0.05 and two-sided 95% confidence intervals (CI) will be calculated. All tests of interactions between treatment groups and other factors will be conducted at a 2-sided alpha level of 0.10, unless otherwise noted. Parametric and nonparametric methods, as determined by the distribution of each variable, will be used to test statistical hypotheses of continuous variables. In the event of highly skewed data, a logarithmic transformation will be considered prior to any statistical testing.

All p-values will be rounded to 3 decimal places. A p-value rounded to 1.000 will be displayed as >0.999, and a p-value rounded to 0.000 will be displayed as <0.001.

Multiplicity will be managed by testing the primary and key secondary endpoints in a hierarchical fashion. All analyses will be performed using data pooled across sites.

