The hazard ratio (HAV relative to ePTFE graft) will be estimated using a Cox proportional hazards regression with treatment group and the surgical placement stratification variable as factors. Based on the estimated event-free rate in the ePTFE graft arm at the data cut-off using Kaplan-Meier method, the non-inferiority margin will be determined by the hazard ratio corresponding to a difference of 10 percentage points. Hazard Ratio (HAV to ePTFE) Margin = $\text{Log}(\text{ePTFE K-M estimated event free rate} - 0.1) / \text{Log}(\text{ePTFE K-M estimated event free rate})$ . For analyses conducted at 12 months, the hazard ratio will be calculated from the ePTFE K-M estimated event-free rate at 12 months. For analyses conducted at 18 months, the hazard ratio will be calculated from the ePTFE K-M estimated event-free rate at 18 months. Similarly, for analyses conducted at 24 months, the hazard ratio will be calculated from the ePTFE K-M estimated event-free rate at 24 months. If the upper limit of the two-sided 95% confidence interval for the hazard ratio is less than the corresponding non-inferiority margin hazard ratio, then non-inferiority will be demonstrated.

The primary analysis will be in the ITT analysis set. The analysis of the primary endpoints of interest will be repeated using the mITT and per-protocol analyses sets as confirmatory.

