### **6.1.1 EFFICACY ANALYSIS AT 24 MONTHS**

The efficacy endpoint is the time to loss of Secondary Patency assessed when all patients are at least 24 months after implantation (or have been censored). The analysis at 24 months will be non-inferiority analysis using the following censoring rules:

- Subjects who have patent study conduits at the time of death, kidney transplant, voluntary withdrawal will be censored at that timepoint
- Subjects who have an abandonment of the study conduit due to improved health that leads to dialysis discontinuation will be censored at the date of abandonment
- Subjects who are lost to follow-up will be censored at their last visit when it was known that the study conduit was patent
- Subjects who are lost to follow up and whose study conduit was not patent at the last completed visit will be treated as abandoned at the time of study conduit occlusion
- Subjects in whom a delayed decision is made to abandon the study conduit (e.g. delayed and then failed thrombectomy) will have the date of abandonment set as the date of the initial recognition of the thrombosis, not the date that a final decision is made
- For subjects who discontinue early or who complete without meeting criteria for the event, the time-to-event will be censored and defined as the number of days from randomization to the subject's last visit during the study

At 24 months, the Restricted Mean Survival Time (RMST) method will be used to evaluate non-inferiority of HAV versus ePTFE for all non-censored subjects in the trial reaching 24 months. The RMST test is commonly employed in the setting of non-proportional hazards. It is well-established that the RMST has greater statistical power than the Cox hazard ratio model when proportionality is violated. ([Kaur, 2018](#)). We will utilize the 730.3 day timepoint (2 years, or 24 months), to calculate the mean survival times (loss of secondary patency) for each treatment group. The Weibull survival model will be first fit to the ePTFE time to loss of secondary patency event times to estimate the shape and scale parameters. These parameter estimates will then be used to derive the non-inferiority margin for the difference in RMST in days between HAV and ePTFE at 24 months, based on the non-inferiority hazard ratio margin determined by the method described above in Section 6.1.

At 24 months, additional efficacy analyses will be performed as follows:

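### The non-inferiority margin is estimated from the trial's own ePTFE arm but treated as known: at planning rates the 24-month RMST test has about 3.5% one-sided error instead of 2.5%, while the primary Cox test is undistorted there but not at other rates

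*SAP*

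**What the plan says.** The constant in the plan is a loss of 10 percentage points. In SAP 6.1, "the non-inferiority margin will be determined by the hazard ratio corresponding to a difference of 10 percentage points", computed as log(S − 0.1)/log(S), where S is the ePTFE event-free rate. S comes from the trial itself: "Based on the estimated event-free rate in the ePTFE graft arm at the data cut-off using Kaplan-Meier method". The time point follows the analysis: "For analyses conducted at 18 months, the hazard ratio will be calculated from the ePTFE K-M estimated event-free rate at 18 months". Protocol 10.3.2 does the same: "Based on the estimated 18-month event-free rate in the ePTFE arm, the non-inferiority margin will be determined by the hazard ratio". (The Protocol words the inequality the other way round; the SAP form, upper limit below the margin, is used here.)

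The primary decision rule in SAP 6.1 begins: "If the upper limit of the two-sided 95% confidence interval for the hazard ratio is less than the corresponding non-inferiority margin hazard ratio". The interval is the ordinary Cox interval.

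For the 24-month RMST analysis, SAP 6.1.1 fits a Weibull model to the ePTFE loss times. "These parameter estimates will then be used to derive the non-inferiority margin for the difference in RMST in days between HAV and ePTFE", together with the hazard-ratio margin from 6.1. Section 6.1.1 states no RMST decision rule. The two-sided 95% interval has to be taken from the general rule in SAP 4.

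Protocol 10.3.3 and SAP 6.2 apply the same approach and margin to Primary Patency non-inferiority, inside the fixed testing sequence. Neither document mentions the margin's sampling error, its covariance with the treatment estimate, or the resulting type I error.

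**The concern.** A two-sided 95% interval compared with a fixed margin gives 2.5% one-sided error. Here the margin is itself an estimate, and the ePTFE patients who determine it also determine the hazard ratio and the RMST difference. The interval therefore has the wrong width for the hypothesis of interest, that HAV loses no more than 10 points.

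The direction depends on how the margin moves with S:

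- **RMST.** An ePTFE arm that does badly by chance improves HAV's difference and also widens the margin in days. Both errors favour passing.
- **Cox.** log(S − 0.1)/log(S) is nearly flat around S = 0.40 to 0.47 and rises on either side. At low S a chance-poor ePTFE arm widens the margin (lenient). At high S it narrows it (strict).

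At stake is whether a non-inferiority statement carries the error rate that its interval implies.

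**Working it through.** **1. The plan's own figure.** SAP 11 gives 90% power for 350 subjects, 60% v 66% at 12 months. The margin is ln 0.50/ln 0.60 = 1.357 and the true HR is ln 0.66/ln 0.60 = 0.813. With 16-month accrual, 12-month minimum follow-up and the ~20% annual death rate of SAP 6.1 as censoring, 158 events are expected. Power = Φ(√158/2 × ln(1.357/0.813) − 1.96) = Φ(3.22 − 1.96) = 89.5%. The 90% is reproduced with the margin taken as known.

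**2. ePTFE rates implied by the documents (exponential extension, an assumption).** From 60% at 12 months: 0.60^1.5 = 46.5% at 18 months and 0.60² = 36% at 24 months. From the lower end of the 50% to 60% at one year in Protocol 2.4.3.3: 0.50^1.5 = 35.4% at 18 months.

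**3. How the margin moves.** The hazard-ratio margin is 1.368 at S = 25%, 1.320 at 35.4%, 1.316 at 46.5%, 1.357 at 60% and 1.598 at 80%. In the exponential case the RMST margin is (1 − S)/λ − (1.1 − S)/(λh), with λ = −ln S/24 and h the hazard-ratio margin. At S = 36%: λ = 0.04257 and h = 1.3185, so 15.03 − 13.18 = 1.85 months, or 56 days. It is 68 days at 25% and 44 days at 65%.

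**4. Simulated error at a true loss of exactly 10 points.** Settings: 175 per arm, 16-month accrual, minimum follow-up 18 or 24 months, exponential loss, proportional hazards, 20% per year death censoring, all randomised subjects with ordinary censoring, placement covariate omitted, 30,000 to 120,000 runs per case (Monte Carlo error about 0.05 to 0.1 point).

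| ePTFE rate at 24 months | RMST, estimated margin |
|---|---|
| 25% | 4.8% |
| 30% | 3.8–3.9% |
| 36% (planning-implied) | 3.5% |
| 45% | 3.1–3.2% |
| 65% | 3.0–3.1% |
| 80% | 3.2% |

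| ePTFE rate at 18 months | Primary Cox, estimated margin |
|---|---|
| 25% | 5.0% |
| 35.4% | 3.2% |
| 46.5% (planning-implied) | 2.5% |
| 60% | 2.0% |
| 80% | 1.2–1.3% |

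With the true margin supplied, both tests return to about 2.5%. Weibull shapes from 0.6 to 1.3 leave RMST at 3.4% to 3.5% at 36%. Removing 10% of subjects for the withdrawn site gives Cox 3.3%, 2.4%, 1.9% and 1.3% at 35.4%, 46.5%, 60% and 80%.

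**5. Hand check.** The written rule behaves like a critical value of 1.96 × (ordinary SE)/(SE of the contrast including the margin).

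- RMST at 36%: 1.96 × 0.970/1.043 = 1.82, tail 3.4%.
- Cox at 35.4%: 1.96 × 0.1300/0.1352 = 1.88, tail 3.0%.
- Cox at 46.5%: 1.96 × 0.1400/0.1385 = 1.98, tail 2.4%.
- Cox at 80%: 1.96 × 0.2115/0.1803 = 2.30, tail 1.1%.

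**6. Primary Patency.** SAP 11 plans 50% at 6 months. Extended exponentially (an assumption), this is 0.50³ = 12.5% at 18 months, with margin ln 0.025/ln 0.125 = 1.774. The formula has no value when the estimate is 10% or less. Without censoring the SE is √(0.125 × 0.875/175) = 0.025, so 10% lies one SE below and is reached about 16% of the time. With death censoring the simulation gives about 19%. Counting those trials as not passing, the rule passes a true 10-point loss about 11% of the time. At assumed rates of 15%, 20% and 25% it passes about 13%, 7.9% and 5%. The ~60% at six months in Protocol 2.1 would extend to 0.60³ = 21.6%, between the last two.

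**The case against.** **The primary test is sound where it was planned.** This stands. At 46.5% the error is 2.5%. A reader might infer that the primary analysis is generally inflated; the documents do not support that. Their ePTFE rates of 50% to 60% at one year imply 35% to 46.5% at 18 months, where the error is about 3.2% to 2.5%. No passage supports 80% for ePTFE, and above 46.5% the test loses power without adding false non-inferiority. Nor are 1.2% and 3.2% bounds: at 25% the error is 5.0%.

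**The RMST test lies outside the controlled family.** Also true. It belongs to the second analysis and is not in the fixed sequence of SAP 6.2, so its excess does not inflate the trial's confirmatory error. The excess is about one percentage point at planning values.

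**The simulated RMST test may not be the written one.** SAP 6.1.1 restricts RMST to subjects who are not censored. If meant literally, that is a different analysis, which was not modelled. RMST is also introduced there for non-proportional hazards, whereas the figures assume proportional hazards. Both points limit the precision of the numbers. They do not remove the dependence between margin and estimate.

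**A bootstrap for the primary rule gains little at the planning rate.** This stands too. Bootstrapping log HR minus log margin gave 1.9%, 2.9% and 2.5% at 35.4%, 46.5% and 80% (3,000 runs, ±0.3 point). Replacing the primary rule is therefore not called for.

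**Conclusion.** The point holds as an interval of the wrong width, with a size that depends on the ePTFE rate.

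- **24-month RMST:** anti-conservative at every rate tested, about 3.5% at the planning-implied 36% and about 3.0% to 4.8% over 80% down to 25%. This assumes proportional hazards, exponential loss, 175 per arm, ordinary censoring and a two-sided 95% interval.
- **Primary Cox at 18 months:** no distortion at 46.5%, mildly lenient at 35%, conservative at higher assumed rates. The error is uncontrolled, not generally inflated.
- **Primary Patency non-inferiority:** potentially the largest effect, and inside the fixed sequence, but it rests on extending 6-month patency exponentially to 18 months. The possibility of an undefined margin follows from the formula alone once the ePTFE estimate reaches 10%.

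The change should be made for RMST and Primary Patency. For the primary test a prespecified sensitivity analysis is enough.

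**What to change.** Keep the 10-point margin.

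1. **SAP 6.1.1.** State the RMST rule: non-inferiority if the lower 95% limit of (RMST HAV − RMST ePTFE + estimated margin in days) is above 0, using all randomised subjects with standard censoring. Take the standard error from a bootstrap within arm and placement stratum that refits the Kaplan-Meier rate, Weibull model and margin in every resample. Name the interval type (for example, normal-based with the bootstrap standard error) and use at least 1,000 resamples. A bootstrap of the ePTFE arm moved the error from 3.7% to 2.7% at 36% and from 3.2% to 2.8% at 65% (4,000 runs, ±0.25 point).
2. **SAP 6.1.** Add, at least as a prespecified sensitivity analysis, either the bootstrap interval for log HR minus log estimated margin, or the direct Kaplan-Meier difference at 18 months against −10 points. The latter had 2.4% to 2.7% error for ePTFE rates from 35.4% to 80%.
3. **SAP 6.2, Primary Patency.** Use the direct Kaplan-Meier difference, which stays defined when the hazard-ratio margin does not. The 2.4% to 2.7% does not cover rates as low as 12.5%, so check its normal approximation there before adopting it.

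Cost: SAP wording and a short program, with no new data or patients. RMST power at the planned effect (66% v 60% at 12 months) falls by about 3 points (89% to 86% in 600 runs).

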### **6.1.1 EFFICACY ANALYSIS AT 24 MONTHS**

The efficacy endpoint is the time to loss of Secondary Patency assessed when all patients are at least 24 months after implantation (or have been censored). The analysis at 24 months will be non-inferiority analysis using the following censoring rules:

- Subjects who have patent study conduits at the time of death, kidney transplant, voluntary withdrawal will be censored at that timepoint
- Subjects who have an abandonment of the study conduit due to improved health that leads to dialysis discontinuation will be censored at the date of abandonment
- Subjects who are lost to follow-up will be censored at their last visit when it was known that the study conduit was patent
- Subjects who are lost to follow up and whose study conduit was not patent at the last completed visit will be treated as abandoned at the time of study conduit occlusion
- Subjects in whom a delayed decision is made to abandon the study conduit (e.g. delayed and then failed thrombectomy) will have the date of abandonment set as the date of the initial recognition of the thrombosis, not the date that a final decision is made
- For subjects who discontinue early or who complete without meeting criteria for the event, the time-to-event will be censored and defined as the number of days from randomization to the subject's last visit during the study

At 24 months, the Restricted Mean Survival Time (RMST) method will be used to evaluate non-inferiority of HAV versus ePTFE for all non-censored subjects in the trial reaching 24 months. The RMST test is commonly employed in the setting of non-proportional hazards. It is well-established that the RMST has greater statistical power than the Cox hazard ratio model when proportionality is violated. ([Kaur, 2018](#)). We will utilize the 730.3 day timepoint (2 years, or 24 months), to calculate the mean survival times (loss of secondary patency) for each treatment group. The Weibull survival model will be first fit to the ePTFE time to loss of secondary patency event times to estimate the shape and scale parameters. These parameter estimates will then be used to derive the non-inferiority margin for the difference in RMST in days between HAV and ePTFE at 24 months, based on the non-inferiority hazard ratio margin determined by the method described above in Section 6.1.

At 24 months, additional efficacy analyses will be performed as follows:

- a. The RMST method will be used to evaluate non-inferiority of HAV versus ePTFE for all non-censored subjects in the trial reaching 18 months. We will utilize the 18-month (547.9 days) timepoint to calculate the mean survival times (loss of secondary patency) for each treatment group.
- b. The RMST method will be used to evaluate non-inferiority of HAV versus ePTFE for all non-censored subjects in the trial reaching 12 months. We will utilize the 12-month (365.25 days) timepoint to calculate the mean survival times (loss of secondary patency) for each cohort.
- c. The RMST method will be used to evaluate non-inferiority of HAV versus ePTFE for all non-censored FEMALE subjects in the trial reaching 24 months.
- d. The RMST method will be used to evaluate non-inferiority of HAV versus ePTFE for all non-censored MALE subjects in the trial reaching 24 months.
- e. The RMST method will be used to evaluate non-inferiority of HAV versus ePTFE for all non-censored FEMALE subjects in the trial reaching 18 months.
- f. The RMST method will be used to evaluate non-inferiority of HAV versus ePTFE for all non-censored MALE subjects in the trial reaching 18 months.
- g. The hazard ratio (HAV relative to ePTFE graft) will be estimated using a Cox proportional hazards regression at 24 months, with right-censoring of data occurring after 24 months (Day 730). Based on the estimated event-free rate in the ePTFE graft arm at the data cut-off using Kaplan-Meier method, the non-inferiority margin will be determined by the hazard ratio corresponding to a difference of 10 percentage points. Hazard Ratio (HAV to ePTFE) Margin = $\text{Log}(\text{ePTFE K-M estimated event free rate} - 0.1) / \text{Log}(\text{ePTFE K-M estimated event free rate})$ . If the upper limit of the two-sided 95% confidence interval for

the hazard ratio is less than the corresponding non-inferiority margin hazard ratio, then non-inferiority will be demonstrated.

- h. The hazard ratio (HAV relative to ePTFE graft) will be estimated for all FEMALE subjects using a Cox proportional hazards regression at 24 months, with right-censoring of data occurring after 24 months (Day 730).
- i. The hazard ratio (HAV relative to ePTFE graft) will be estimated for all MALE subjects using a Cox proportional hazards regression at 24 months, with right-censoring of data occurring after 24 months (Day 730).
- j. The hazard ratio (HAV relative to ePTFE graft) will be estimated for all FEMALE subjects using a Cox proportional hazards regression at 24 months, WITHOUT right-censoring of data occurring after 24 months.
- k. The hazard ratio (HAV relative to ePTFE graft) will be estimated for all MALE subjects using a Cox proportional hazards regression at 24 months, WITHOUT right-censoring of data occurring after 24 months.

The primary analysis will be in the ITT analysis set. The analysis of the primary endpoints of interest will be repeated using the mITT and per-protocol analyses sets as confirmatory if the mITT or the PP analysis set is different from the ITT analysis set.

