## 4.2 ANALYSIS SETS

The primary analysis will be based on the Intent-to-Treat (ITT) analysis set defined as all randomized subjects (based on study conduit group assignment).

The following rules will apply to the ITT analysis set:

- Subjects in whom the wrong conduit is implanted (e.g. an HAV implanted in a subject randomized to an ePTFE graft) will be analyzed within their randomized group rather than in their implanted group
- Subjects in whom no study conduit was implanted will be considered as if abandoned on Day 0 and included in their randomized group
- Subjects in whom the site (upper vs forearm) of implantation is different from the intended site will be analyzed based on the intended site.

The analysis will be repeated using the modified Intent-to-Treat (mITT) analysis set defined as all subjects in whom a study conduit has been implanted (based on actual conduit implanted and the actual site).

A secondary analysis will be conducted in a Per Protocol (PP) analysis set defined as all subjects in whom a study conduit has been implanted (based on actual conduit implanted) and in whom there were no major protocol deviations or data integrity concerns.

Major protocol deviations will be reviewed and verified at the time of determination, the time between the database soft lock and hard lock. Humacyte will identify major protocol deviation categories prior to the close of the database for the primary, second and final analysis. An overall major protocol deviation listing will be reviewed just prior to database lock for final analysis. Humacyte will approve all final major protocol deviation determinations. The protocol deviations SAS dataset will then be generated but will not be entered into the database.

Safety analysis will be conducted using the safety analysis set, which is defined as all subjects who receive study treatment, with the subject's treatment group based on the treatment that was received.

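### SAP 6.1.1 states all seven RMST non-inferiority tests for non-censored subjects, which conflicts with its own censoring rules and with the ITT set

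*SAP*

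**What the plan says.** SAP 6.1.1 opens with censoring rules for the 24-month analysis. The first reads "Subjects who have patent study conduits at the time of death, kidney transplant, voluntary withdrawal will be censored at that timepoint". The last gives early discontinuers and event-free completers a censored time that ends at their last visit. The section closes with "The primary analysis will be in the ITT analysis set", repeated in mITT and PP where these differ. SAP 4.2 describes the ITT "analysis set defined as all randomized subjects (based on study conduit group assignment").

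Between these statements, the main 24-month RMST method is to "evaluate non-inferiority of HAV versus ePTFE for all non-censored subjects in the trial reaching 24 months". Item a is stated "for all non-censored subjects in the trial reaching 18 months", item b has the same form at 12 months, and item c is stated "for all non-censored FEMALE subjects in the trial reaching 24 months". Items d to f follow that pattern by sex and horizon. That makes seven RMST tests with the restriction. The Cox items in the same list (g to k) do not have it; h to k refer simply to all female or all male subjects.

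For the margin, a Weibull model is fitted to the ePTFE data and combined with the hazard-ratio margin of SAP 6.1 "to derive the non-inferiority margin for the difference in RMST in days between HAV and ePTFE at 24 months".

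**The concern.** A rule that censors a subject at death or transplant keeps that subject in the analysis up to that date. A restriction to non-censored subjects removes the subject. Both cannot hold, and the restricted set is not the ITT set. Only the RMST items carry the restriction, so a programmer has grounds in the text for building a different population for them.

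The phrase has at least three literal readings:

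1. Events only, because the section's last rule also censors event-free completers.
2. Drop anyone censored before the horizon, and keep failures and subjects still patent at the horizon.
3. Keep only subjects followed to the horizon, whatever their patency.

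Each selects on an outcome or on follow-up after randomisation. The subjects lost under reading 2 all had patent conduits when they left, while every observed failure stays in. The choice also feeds the margin, because both the ePTFE Kaplan-Meier rate and the Weibull fit change with the set. Protocol 10.3 describes no RMST analysis that could settle the matter.

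**Working it through.** **Inputs.** From SAP 11: 350 subjects 1:1 (175 per arm), ePTFE 60% event-free at 12 months, design alternative HAV 66%. From SAP 6.1: annual death rate of about 20%, and hazard-ratio margin log(S − 0.1)/log(S). Assumed: exponential event and loss times, with losses of 20% a year independent of patency.

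**The plan's own figure.** The SAP gives no power or margin in days for RMST. Its 90% power for Cox non-inferiority can be checked. The margin is ln 0.5/ln 0.6 = 1.357 and the true hazard ratio is ln 0.66/ln 0.6 = 0.813. With 16 months' accrual, 12 months' minimum follow-up and 20% yearly deaths censored, about 158 events are expected. Power = Φ(√(158/4) × (ln 1.357 − ln 0.813) − 1.96) = 89.5%. The inputs are therefore in line with the design.

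**Margin in days at 24 months, all ePTFE subjects.** S = 0.6² = 0.36, so the hazard-ratio margin is ln 0.26/ln 0.36 = 1.3185. RMST to 730.3 days is 457.5 days for ePTFE and 401.2 days at the margin, a difference of 56.3 days. It is 56 to 58 days for Weibull shapes 0.7 to 1.3.

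**Reading 1 (events only).** No one remains patent at the horizon. Patency at 24 months cannot be estimated, and log(S − 0.1) does not exist at S = 0.

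**Reading 2 (drop censored).** The event hazard is −ln 0.6 = 0.511 and the loss hazard −ln 0.8 = 0.223 per year. ePTFE share dropped = 0.223/0.734 × (1 − e^(−0.734 × 2)) = 23.4%. In what remains, ePTFE patency at 24 months falls from 0.36 to 0.30. The hazard-ratio margin becomes ln 0.20/ln 0.30 = 1.337, and the margin in days widens to about 62.6.

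**Reading 3 (followed to 24 months).** 0.8² = 0.64 of each arm stays: 0.64 × 175 = 112.

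**Simulation.** Kaplan-Meier RMST with a Greenwood-type variance; non-inferiority if the lower 95% limit of HAV minus ePTFE lies above the negative margin. Equal 20% losses, 24 months:

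| Subjects analysed | Margin | False non-inferiority, HAV at the margin | Power, 66% vs 60% |
|---|---|---|---|
| All ITT, right-censored | re-estimated | 3.6% | 88% |
| Censored dropped | re-estimated, same set | 6.1% | 86% |
| All ITT, right-censored | fixed, 56 days | 2.4% | 90% |
| Censored dropped | fixed, 56 days | 3.0% | 84% |
| Followed to 24 months only | fixed, 56 days | 2.6% | 78% |

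Independent repeats agree to about 1.5 points for power and half a point for error rates. The re-estimated rows are closest to the SAP, which derives its margin from the trial's own ePTFE data. With the margin re-estimated, power in the last row is about 77%.

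**Range of losses.** In a smaller run (1,000 trials per scenario, margin from an exponential fit to the reduced set), yearly losses of 10%, 20% and 30% gave false non-inferiority of 3.7%, 4.8% and 8.6% with censored subjects dropped, against 3 to 4% in the ITT set.

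**Unequal losses (assumed).** With ePTFE/HAV losses of 25%/15% and HAV at the margin, reading 2 shrinks the mean difference from −56.1 to −30.9 days. False non-inferiority is about 12% with a fixed margin and about 21% re-estimated. With 15%/25% it is 0.3% (fixed margin). Reading 3 gave 2.3% at 25%/15%.

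**The case against.** The best reply is that the wording is loose and exclusion was never meant. The section says its analysis uses the listed censoring rules and names ITT; dropping censored subjects would make both pointless. SAP 1 and 4 define the 24-month data cut as every subject having reached 24 months or been censored, and the phrase may be a garbled echo of that condition. This stands as far as it goes: the documents show a conflict to reconcile, not that subjects will be dropped. It does not remove the conflict, because the restriction appears seven times and only in the RMST items.

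Four stronger inferences are tempting, and the documents do not support them.

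- *There is no RMST decision rule.* SAP 6.1.1 derives a margin, SAP 4 sets two-sided 95% intervals by default, and SAP 6.1 gives both the pattern of comparison and the hazard-ratio margins at 12 and 18 months. Detail is missing, not the rule.
- *The 24-month tests are put forward as confirmatory.* Item g does end with "the corresponding non-inferiority margin hazard ratio, then non-inferiority will be demonstrated", but the SAP calls this a second analysis, lists a to k as additional, and controls multiplicity only for the primary and key secondary endpoints.
- *The restriction mainly costs power.* That is so with a fixed margin, or if only subjects followed to 24 months are kept. If censored subjects are dropped and the margin is re-estimated from the same set, power barely moves and the false-positive rate rises.
- *The comparison is biased.* Bias of any size under reading 2 needs losses that differ by arm. SAP 6.1 expects similar death rates, so this is a sensitivity case. Under reading 3 it did not appear with independent losses.

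**Conclusion.** The population conflict holds and should be fixed. Two competent programmers could build different analysis sets, and from them different margins, for all seven RMST tests. Under the stated assumptions the most damaging workable reading moves false non-inferiority at 24 months from about 3.6% to about 6%; the other workable reading costs 10 to 12 points of power. The events-only reading cannot be carried out. These sizes rest on exponential times, 20% yearly losses in both arms and losses independent of patency; the unequal-loss figures rest on a further assumption.

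The point is limited to the RMST analyses in SAP 6.1.1. The 18-month primary Cox analysis and the key secondary sequence do not use this wording.

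**What to change.** In SAP 6.1.1, main text and items a to f, replace the restriction to non-censored subjects reaching X months with: *all subjects in the analysis set (ITT; repeated in mITT and PP; by sex for items c to f), right-censored under the rules above, with RMST taken as the area under the Kaplan-Meier curve to X months.*

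State that the Weibull margin model is fitted to all ePTFE subjects in that set, censored times included, and converted to days with the SAP 6.1 hazard-ratio margin for the same horizon.

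As a clarification only, add that non-inferiority requires the lower 95% limit of the RMST difference (HAV minus ePTFE) to exceed the negative margin.

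The cost is SAP wording. No new data are needed. If the RMST analyses have already been run on a restricted set, they need to be re-run.
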